3.2 Rationale for Study Design and Dose Level

3.2.1 Rationale for Dose Level

3.2.1.1 Determining Therapeutic Levels of an Anti-endotoxin Therapeutic

It is hypothesized that continuous administration of opebacan therapy will provide continuous drug levels that will be available to neutralize circulating endotoxin and ameliorate endotoxin mediated activation of the innate immune system, thus preventing or reducing complications associated with endotoxemia, including aGvHD.

While absolute quantities of total endotoxin can be measured in the blood by limulus amoebocyte lysate (LAL) assays, quantitative measurements of the unbound fraction that is functional (i.e., inflammatory) are difficult to obtain because of the following:

- 1. The lipid A moiety of endotoxin can form micelles, as well as interact specifically with LBP and TLR4 and non-specifically with many biological molecules and structures (e.g., HDL, albumin and cell membranes). Each of these varied interactions affects endotoxin function, clearance, and area-under-the curve quantities.
- 2. Endotoxin typically enters the blood stream erratically, either from disruption of the gastrointestinal (GI) or urinary tract, or manifest clinically as bacteremia, and thus tends to result in erratic blood levels (and clinical manifestations) over time.
- 3. Circulating endotoxin is not one discrete molecule, but is always a complex mixture, with each bacterial serotype making its own unique combination of lipid A and carbohydrate backbone. Thus, endotoxin molecules have a wide range of affinities for specific receptors depending, in part, on the specific lipid A structure and the length of the carbohydrate backbone.

As a result, unbound endotoxin levels in the blood are almost impossible to reliably measure or model with any degree of clinical assurance. This lack of information makes the process of determining the target level of an endotoxin-neutralizing substance needed for a desired clinical effect very challenging.

For example, attempts at XOMA to model appropriate doses of opebacan to neutralize endotoxin based on *in vitro* and *in vivo* studies have resulted in estimated opebacan blood levels as high as 10 µg/mL—a level which, although safe when given in short infusions, is both clinically impractical and poses possible safety issues if given continuously over extended time periods. On the other hand, evidence of clinical activity, including significant and trending prospective measures of clinical benefit, were observed in a randomized, double-blinded trial in pediatric meningococcemia with 2 mg/kg opebacan administered continuously over 24 hours, yielding steady-state plasma levels of 67 ng/mL.

These mixed results suggest that establishing a dosing rationale for opebacan that seeks efficacy signals while maximizing safety will require the use of a composite of quantitative safety observations from animal toxicology studies, other animal data, and human experience and empirical observations in this population.

3.2.1.2 An Endotoxin Antagonist in an aGvHD Animal Model: Clinical Study Considerations

[figure not shown]
Cooke and colleagues evaluated an endotoxin antagonist (a synthetic lipid-A analogue) in a mouse aGvHD model (Cooke et al., 2001). Results from this study demonstrated that a course of endotoxin antagonist given for six days significantly reduced the later onset of aGvHD. In this animal model, the drug did not need to be present at the time when aGvHD was expected to occur, but rather before onset of aGvHD in a prophylactic mode. If opebacan prophylaxis proves useful in humans receiving stem cell transplants, the duration of such prophylaxis will need to be empirically determined since onset of aGvHD in humans starts between post-transplant Days 21 and 42, later than reported in the mouse model.

Prior to receiving the stem cell transplant, patients undergo an intensive conditioning regimen to destroy benign and, in some cases, malignant cells of the lymphoid and hematopoietic compartments. This regimen also kills other rapidly dividing normal cells, such as the epithelial cells lining the GI tract and their precursors. Data in mice indicate the damage to the GI epithelium results in leakage of bacterial endotoxin from the GI tract into the systemic circulation. This systemic endotoxin exposure has been linked to a concomitant inflammatory response that amplifies the donor anti-host T cell activities with resultant worsening of aGvHD (Cooke et al., 1998). Furthermore, when an endotoxin antagonist was administered from Day 0 through Day +6 after transplant, the severity of aGvHD was significantly reduced without evidence of any other interference with T cell function and the duration of leukemia-free survival was prolonged (Cooke et al., 2001). These results support the use of opebacan, an endotoxin antagonist, as a therapeutic agent to prevent aGvHD and suggest that this approach has potential to reach separate effects on GvHD from those on GvL.

3.2.1.3 Endogenous BPI and LPS Levels Following Hematopoietic Stem Cell Transplant

Levy, [name] and colleagues, and XOMA are presently conducting a study to investigate the endogenous background levels of BPI and LPS in patients undergoing HSCT. Recent human data have shown that, post-conditioning, patient blood levels of endogenous BPI drop to undetectable levels rapidly as the ANC falls. During this period there is a concomitant rise in LBP (indicating endotoxemia); furthermore, as neutrophils recover in these patients, circulating levels of BPI rise and LBP diminish to normal pre-inflammatory levels (Levy, [name], et al., unpublished observations, Figure 2).

Figure 2
Plasma Concentrations in Patients Undergoing HSCT

Based on all of the above, it is hypothesized that continuous administration of opebacan therapy to provide continuous drug levels, before infusion of donor cells, will make BPI available to neutralize circulating endotoxin and ameliorate endotoxin-mediated activation of the innate immune system, thus preventing or reducing complications associated with endotoxemia, including aGvHD.

3.2.1.4 Nonclinical Safety Assessment Summary

The general toxicity of opebacan was assessed in the rat and the monkey using the IV route of administration (bolus administration, continuous and intermittent infusion) for up to 28 days. Doses evaluated in these studies ranged from 2 to 200 mg/kg/day in the rat and from 10 to 200 mg/kg/day in the monkey.

[figure not shown]
Dose-related myocardial toxicity was observed in a single rat and a single monkey study following continuous infusion of formulated opebacan at ≥ 100 mg/kg/day for 3 to 5 days. No cardiotoxicity was seen in a number of other studies where formulated opebacan was continuously administered at doses up to 120 mg/kg/day in the rat and up to 75 mg/kg/day in the monkey for the same or longer duration, and where formulated opebacan was administered intermittently 4 times a day for 28 days at doses up to 150 mg/kg/day in the rat and up to 100 mg/kg/day in the monkey. The later data suggests that the duration of exposure may pose a greater risk of cardiac toxicity than the total daily dose.

Steady-state plasma opebacan levels were calculated for the rat and monkey studies where cardiotoxicity was evident. In the rat study, the steady-state plasma opebacan level corresponding to the cardiotoxic dose was approximately 3 µg/mL, and the no-observed-

adverse-effect-level (NOAEL) dose was approximately 1 μ g/mL. These plasma values were determined using data from a rat pharmacokinetics study. Analysis of the data from the monkey study showed that the cardiotoxic dose for steady-state opebacan level in the monkey was 23 μ g/mL. The steady-state plasma opebacan level corresponding to the NOAEL dose (10 μ g/mL) was calculated using data from this study as well as from another study where 75 mg/kg/day was continuously infused for 28 days.

Based on these toxicology studies, a maximum desirable steady-state plasma concentration of 1 μ g/mL was selected for this study. Using this steady-state level, estimates from human modeling of trauma subjects indicate that a dose of 24 mg/kg/day by continuous infusion should provide a blood level approaching 1 μ g/mL (see Figure 3).

Figure 3
Plasma Concentration-time of Opebacan for Dosing Regimens in HSCT Subjects

With this in mind, the rationale for the various components of the dosing regimens selected for this trial is as follows:

1. Initial loading dose of 4 mg/kg \times 30 minutes:

The initial dose of opebacan is meant to provide a transient high level of drug to initiate endotoxin neutralization and begin to replace missing natural BPI (decreased due to neutropenia from the conditioning regimen). This dose was selected because it gives transient high blood levels and is supported as safe by both animal toxicology data and human experience.

2. Initial starting continuous dose of 6 mg/kg/day \times 3 days:

The maximum dose of opebacan administered in humans in prior trials (hemorrhagic trauma) was 6 mg/kg/day \times 3 days by continuous IV infusion, with no reported drug toxicities. The steady-state plasma levels following this regimen were about 250 – 280 ng/mL. According to XOMA's pharmocokinetic modeling, this dose is a quarter of the dose estimated to yield a steady-state plasma level of 1 μ g/mL, the NOAEL in animal models.

3. Escalation to 12 mg/kg/day \times 3 days:

This dose is expected to give half the calculated dose capable of achieving the maximum desirable blood level (1 μ g/mL).

4. Escalation of infusion duration from 3 to 7 days (12 mg/kg/day \times 7 days):

This infusion duration is approximately double the previous dose and half the proposed highest dose duration of 14 days. Neutropenia is expected to last well beyond 7 days.

5. Escalation of infusion duration from 7 to 14 days (12 mg/kg/day \times 14 days):

Continuous IV studies in rats and monkeys for 14 and 28 days have been completed. In rats, the NOAEL for cardiotoxicity was 50 mg/kg/day following continuous infusion for 14 days, with a steady-state plasma level of about 1 μ g/mL. In monkeys, the NOAEL was 75 mg/kg/day for continuous infusion for 28 days, and yielding plasma levels about 10 μ g/mL. Thus, these studies support 14-day continuous infusion in patients at doses that yield similar steady-state plasma levels. A dose of 12 mg/kg/day for 14 days is expected to yield plasma levels of about 0.5 μ g/mL.

3.2.2 Rationale for Study Design

Opebacan has a well-established safety profile based on other trials but has never been administered to this patient population. Thus, a phase I/II open label, dose- and duration-escalation trial appears to be the appropriate trial design for ensuring an adequate safety margin while testing the hypothesis that opebacan may neutralize circulating endotoxin and thereby benefit stem cell transplant patients.

3.3 Selection of Doses Used in the Study

3.3.1 Dosing Groups

Eligible subjects in five successive dose groups of six subjects each will be treated with opebacan at the dose levels and dose durations shown in Table 1. All subjects will receive a 4 mg/kg continuous IV infusion for 30 minutes. Subjects enrolled in Dose Groups 1, 2, and 3 will then receive a continuous IV infusion at 6 (Group 1), 9 (Group 2) or 12 mg/kg/day (Group 3) for 3 days. For subjects in Dose Groups 4 and 5, the original rapid infusion will be followed, by a continuous IV infusion at 12 mg/kg/day for 7 (Group 4) or 14 (Group 5) days.

Subjects whose conditioning regimen includes total body irradiation (TBI) will have three 1-hour interruptions in their opebacan infusions (one on Day –1 and two on Day 0) to accommodate TBI treatment. Following the final interruption on Day 0, the infusion must be restarted at least 2 hours prior to the HSCT.

3.3.2 Definition and Management of Dose-limiting Toxicity

A DLT is defined as a toxicity of CTC grade 3 or greater severity (based on CTCAE Version 3.0) that is deemed by the Investigator related to the investigational agent, occurs within 4 weeks of administration, and is confirmed by the Investigator and Sponsor, or by the DSMB. A toxicity of CTC grade 2 that is deemed by the Investigator related to the investigational agent and occurs within 4 weeks of administration may also be reported as a potential DLT if the Investigator considers it a clinically significant safety concern.

Given the long list of expected toxicities experienced by patients undergoing HSCT, careful determination of attribution will be particularly important (see Section 5.2).

Sites must notify the Sponsor within 24 hours of having knowledge of a potential DLT. In cases where it is not clear whether an event should be considered related, the Investigator should discuss the case with the Sponsor's medical monitor. Within 24 hours of notification of a potential DLT, the Sponsor will contact the Investigator to discuss the event and together will confirm if it is a DLT. If it is determined that an AE meets all of the criteria for DLT, the subject will discontinue study drug. After receiving treatment for the toxicity (if necessary), the subject will be closely monitored until the toxicity is resolved to no worse than grade 2 severity (grade 1 if reported toxicity is initially grade 2) or is stabilized, at which point he/she will be removed from the study.

If the Investigator and Sponsor cannot agree on the determination of a DLT, the issue will be escalated to the DSMB and the subject will discontinue study drug. Within 7 days of the Sponsor receiving notification of a potential DLT, the DSMB must convene (most likely by teleconference) to determine whether the event is to be classified as a DLT. After receiving treatment for the toxicity (if necessary), the subject will be closely monitored until the

toxicity is resolved to no worse than grade 2 severity (grade 1 if reported toxicity is initially grade 2) or is stabilized, at which point he/she will be removed from the study.

The Sponsor will provide written notification of all DLT determination decisions to the Investigator and DSMB members.

Dose escalation must be delayed until a confirmed DLT has resolved or stabilized at grade 2 (grade 1 if reported toxicity is initially grade 2) or less. All Investigators in the study will be notified of all reported toxicities at each dose level before escalation. The Investigators, Sponsor, and DSMB must agree that proceeding with dose/duration escalation is appropriate before the first subject can be treated in the next study group.

The DSMB will be an independent, interdisciplinary body with four members, including two oncologists, one additional specialist (possibly a cardiologist), and XOMA's biostatistician. The DSMB collectively will have substantial experience in the treatment of subjects undergoing HSCT and in the conduct and monitoring of randomized clinical trials. A full description of the DSMB's responsibilities and procedures will be provided in the DSMB Charter under separate cover.

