After all subjects in a dose group have completed study procedures through Day 28, all available safety information will be reviewed by the DSMB. Dosing may begin for the next dose group at the next higher dose level if no more than one subject in the previous group has experienced a DLT (see Section 3.3.2 for the definition of DLT) and, in the opinion of the DSMB, there are no clinically significant safety concerns at the previous dose level.

All subjects will have disease status, performance score, and cumulative aGvHD status confirmed on Day 100 (± 14 days) by clinic visit, if possible, or by phone. Safety will be assessed by pre- and post-treatment serial measurements of vital signs and clinical laboratory assessments and by the recording of adverse clinical events, with an emphasis on infectious and non-infectious regimen-related toxicities. PK data will be collected and analyzed to determine dose/duration relationships and to explore preliminary correlations of PK data with demographic information, clinical course through transplant, occurrence of transplant regimen related toxicities including aGvHD, and laboratory markers of inflammation. Figure 1 outlines the study design.

Figure 1

- The visit window for Days 21, 28, 42, and 49 is \pm 3 days. The visit window for Day 100 is \pm 14 days.
- IV infusion with opebacan will begin on Day -1, 18 to 36 hours prior to the HSCT. Prior to opebacan dosing, the Principal Investigator or designee must confirm and document that the subject meets all eligibility criteria for the HSCT and that the initiation of study drug administration will precede donor cell administration by 18 to 36 hours. Subjects whose conditioning regimen consists of chemotherapy only will receive a continuous opebacan infusion following completion of chemotherapy treatment on Day -1. Subjects whose conditioning regimen includes total body irradiation (TBI) will have three 1-hour interruptions in their opebacan infusions (one on Day -1 and two on Day 0) to accommodate TBI treatment. Following the final interruption on Day 0, the infusion must be restarted at least 2 hours prior to the HSCT.
- The HSCT will be performed on Day 0, 18 to 36 hours following initiation of opebacan treatment, and no less than 18 hours after the completion of chemotherapy treatment.
- All subjects will have disease status, performance score, and cumulative aGvHD status confirmed on Day 100 (± 14 days) by clinic visit, if possible, or by phone.

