3.3.4 Dose Escalation Plan

Subjects will be enrolled sequentially according to the dose escalation diagram shown in Figure 4. If a DLT occurs in any subject, it must be treated, if necessary, and monitored until it stabilizes or recovers to no worse than CTC grade 2 toxicity (grade 1 if reported toxicity is initially grade 2) prior to additional enrollment. Subjects will be monitored for toxicity with assessments listed in Appendix 1 (Schedule of Assessments).

To minimize the chance of simultaneous graft failures possibly due to exposure to opebacan, only two subjects may be simultaneously enrolled in any dose group until one of them successfully engrafts, defined as ANC $\geq 500/\mu L$ for three consecutive days, with the first day (the day of engraftment) occurring no later than Day 28. Once engraftment occurs in one of the first two subjects in a dose group, the third subject may be enrolled. When engraftment occurs in a second subject within a dose group, the fourth subject may be enrolled, and when

engraftment occurs in a third subject in a dose group, the fifth subject may be enrolled. Finally, when engraftment occurs in a fourth subject in a dose group, the sixth subject may be enrolled.

After all subjects in a dose group have completed study procedures through Day 28, all available safety information will be reviewed by the DSMB. Dosing may begin for the next dose group at the next higher dose level if no more than one subject in the previous group has experienced a DLT and, in the opinion of the DSMB, there are no clinically significant safety concerns at the previous dose level. If, in the opinion of the DSMB, there are clinically significant safety concerns, the DSMB may recommend that the study be discontinued.

If graft failure occurs in any dose group, that dose group will be expanded to 12 subjects. If a second graft failure occurs in the expanded cohort, the DSMB will determine if the study should be stopped after looking at the data for the two subjects whose grafts failed. As with other dose groups, enrollment in the expanded cohort will be staggered to minimize the chance of multiple graft failures. Only two subjects may be simultaneously enrolled until one of them successfully engrafts, at which time an additional subject may be enrolled.

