3.5 Enrollment

Once prescreening is completed and subject eligibility is confirmed, a subject will be assigned a subject number by the Sponsor. Donors who sign an informed consent will be assigned a tracking number that can be used for tracking donor samples and will link those samples with the subject who received the donor's stem cells.

Sites must contact the following individual for subject number assignment:

[name] [contact]

[contact]

Eligible subjects will be assigned to one of five successive dose groups of six subjects each (see Section 3.1 and Table 1). Enrolled subjects who discontinue the trial prior to receiving opebacan will be replaced. Subjects will also be replaced if they do not receive at least 80% of their scheduled dose of opebacan and/or do not complete assessments for at least 7 days following the end of their opebacan infusion.

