4.3 Study Assessments

Study assessments are shown in the Schedule of Assessments (Appendix 1). Routine laboratory analyses, including chemistries, CBC, coagulation measures, and urinalysis will be performed locally at the study sites. Surface markers requiring same day analysis (e.g., TLR4) will also be processed and analyzed locally, though in some circumstances these samples may be frozen, batched and sent to a central lab. All other samples will be analyzed at a central lab.

The following assessments will be performed daily from Day –1 until Day 49 or until the subject is released from the hospital, whichever occurs first:

- Metabolic assessment (Intake and output [I&O] and total days of parenteral nutrition [TPN] only). Assessments requiring daily totals should be measured by calendar day (i.e., from midnight to midnight) unless otherwise specified by institutional standard practice.
- Vital signs including pulse, blood pressure (systolic/diastolic), respiratory rate, and temperature taken in the morning (i.e., the first waking set of vital signs). If a subject experiences an SAE, vital signs must be taken more frequently, per standard institutional practice.

In addition, the oral mucositis score must be recorded at prescreening and then daily from Day –1 through Day 7 (see Appendix 5 for grading scale). After Day 7, the oral mucositis score must be recorded daily until the condition resolves to grade 0. If oral mucositis reappears after resolving, daily assessments must be reinstituted through Day 49 or until the subject is released from the hospital, whichever occurs first.

All assessments scheduled on Days 14, 21, and 28 must be performed for all subjects whether or not the subjects have been discharged from the hospital. Assessments scheduled on Days 35, 42 and 49 will be performed only for those subjects who are still hospitalized on those days. Note that assessments scheduled between Day 14 and Day 49 (excluding Days 21, 28, 35, and 42) are not shown in the table for Appendix 1 (Study BPSC030 Schedule of Assessments), though they are mentioned in the footnotes for the assessments that are affected (i.e., Footnote 14 [metabolic assessment], Footnote 15 [vital signs], and Footnote 21 [oral mucositis]).

Several of the assessments performed during this study are considered "over and above" those normally performed as part of routine patient care for HSCT procedures. These special assessments are as follows:

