4.5 Discontinuation

4.5.1 Subject Discontinuation

Subjects may withdraw or be withdrawn from the study at any time. Every effort should be made to obtain complete follow-up information on subjects who receive any amount of opebacan and discontinue from the study prematurely. The reason(s) for a subject's discontinuation from the study must be clearly documented in the subject's medical records and on the CRF

A subject who experiences DLT at any dose level will discontinue study drug. After receiving treatment for the toxicity (if necessary), the subject will be closely monitored until the toxicity is resolved to no worse than grade 2 (grade 1 if reported toxicity is initially grade 2) severity or is stabilized, at which point he/she will be removed from the study.

In the event that a subject discontinues participation in the study prior to receiving opebacan, the subject will be replaced. No follow-up or additional procedures will be performed on subjects discontinuing prior to receiving opebacan.

Subjects will also be replaced if they do not receive at least 80% of their scheduled dose of opebacan and/or do not complete assessments for at least 7 days following the end of their opebacan infusion.

If the subject discontinues participation in the study after receiving any amount of opebacan, every effort should be made to complete as many subsequent protocol evaluations as possible.

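### The 4-week DLT window has no stated anchor, and the 7-day replacement threshold lets a partly observed subject enter the at-most-1-in-6 rule as DLT-free

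*Supplement*

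**What the plan says.** Five passages govern the DLT count.

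- **Window (section 3.3.2).** A DLT is a confirmed toxicity of sufficient grade that is judged "related to the investigational agent, occurs within 4 weeks of administration". The drug is given over 3, 7 or 14 days, and no section says which day starts the clock.
- **Replacement (sections 3.5 and 4.5.1).** "Subjects will also be replaced if they do not receive at least 80% of their scheduled dose", or if they "do not complete assessments for at least 7 days following the end of their opebacan infusion". No other rule removes a dosed subject from the six.
- **MTD (section 3.3.3).** At least six subjects must finish the treatment course with at most one DLT. No length of DLT follow-up is required.
- **Review (section 3.3.4).** "After all subjects in a dose group have completed study procedures through Day 28, all available safety information will be reviewed by the DSMB". The Figure 1 notes in section 3.1 allow slack: "The visit window for Days 21, 28, 42, and 49 is" ± 3 days, so the visit may fall on Day 25 to Day 31.
- **Table 2 (section 3.3.4).** Escalation probabilities are binomial, for at most one DLT in six subjects who share one DLT rate.

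No section defines a DLT-evaluable subject.

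**The concern.** The escalation rule and the MTD are both counts of DLTs among six. A subject last seen 7 days after infusion passes the replacement test and satisfies the MTD wording, yet most or part of that subject's 4-week window may be unobserved. If such a subject has had no DLT so far, the natural consequence is a DLT-free entry in the denominator. Every such entry pushes the rule towards escalating.

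The replacement rule also conflicts with the review rule. One tolerates 7 days of follow-up after infusion; the other waits until every subject in the group has completed Day 28. The plan does not say which prevails when a subject leaves in between.

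The review itself may be early. If the window runs from the end of infusion, it is still open on Day 28 in every group. This matters most where duration is the thing being escalated: section 3.2.1.4 says the animal data suggest that "the duration of exposure may pose a greater risk of cardiac toxicity than the total daily dose", and the steps to Groups 4 and 5 lengthen the infusion without changing the daily dose.

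**Working it through.** **Inputs from the plan.** Six subjects and at most one DLT (section 3.3.4). Infusion starts on Day −1 and ends on Day 2, 6 or 13 (Appendices 1 and 2). The replacement threshold is 7 days after infusion, and the Day 28 visit has a ± 3 day window. **Assumptions not in the plan:** the true DLT risk *p*, the number of subjects lost, and onset that is uniform (alternatively, constant hazard) from start of infusion to close of window.

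**1. Table 2.** P(≤1 of 6) = (1−p)^6 + 6p(1−p)^5. At p = 0.30 this is 0.1176 + 0.3025 = 0.4202, as printed. All eight rows reproduce to four decimals. The formula gives every subject the full risk *p*, so it presumes complete follow-up.

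**2. Day arithmetic.** Let L be the infusion length in days.

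| | Groups 1–3 | Group 4 | Group 5 |
|---|---|---|---|
| L | 3 | 7 | 14 |
| End of infusion (−1 + L) | Day 2 | Day 6 | Day 13 |
| Last seen at the 7-day threshold | Day 9 | Day 13 | Day 20 |
| Window closes, end anchor | Day 30 | Day 34 | Day 41 |
| Unobserved at threshold, end anchor | 21 days | 21 days | 21 days |
| Window closes, start anchor | Day 27 | Day 27 | Day 27 |
| Unobserved at threshold, start anchor | 18 days | 14 days | 7 days |
| Day 28 review early by, end anchor (visit on Day 25; Day 31) | 2 (5; 0) | 6 (9; 3) | 13 (16; 10) |
| Day 28 review early by, start anchor (visit on Day 25; Day 31) | 0 (2; 0) | 0 (2; 0) | 0 (2; 0) |

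**3. Effect of the 7-day threshold.** A subject lost there shows a DLT with probability q = p·f. Here f = (L+7)/(L+28) for the end anchor (10/31, 14/35, 21/42) and f = (L+7)/28 for the start anchor (10/28, 14/28, 21/28).

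- One lost: P = (1−q)[(1−p)^5 + 5p(1−p)^4] + q(1−p)^5.
- Two lost: P = (1−q)²[(1−p)^4 + 4p(1−p)^3] + 2q(1−q)(1−p)^4.

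Example for Groups 1–3, end anchor, p = 0.30: q = 0.30 × 10/31 = 0.0968. One lost gives 0.9032 × 0.5282 + 0.0968 × 0.1681 = 0.493. Two lost give 0.8158 × 0.6517 + 0.1749 × 0.2401 = 0.574.

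| p = 0.30 (full follow-up 0.420) | Groups 1–3 | Group 4 | Group 5 |
|---|---|---|---|
| End anchor, one lost | 0.493 | 0.485 | 0.474 |
| End anchor, two lost | 0.574 | 0.555 | 0.532 |
| Start anchor, one lost | 0.490 | 0.474 | 0.447 |
| Start anchor, two lost | 0.565 | 0.532 | 0.475 |

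With constant hazard, q = 1 − (1−p)^f, and the end-anchor ranges become 0.469–0.489 (one lost) and 0.522–0.564 (two lost). At p = 0.20 with uniform onset and the end anchor, 0.655 becomes 0.696–0.711 and 0.737–0.766. At p = 0.40, 0.233 becomes 0.285–0.304 and 0.346–0.390.

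**4. Effect of the Day 28 review (end anchor, Group 4).** Day −1 to Day 28 is 29 days of a 35-day risk period. Section 3.3.4 admits the sixth subject only after a fourth has engrafted. If that engraftment is on Day E, the fourth subject is at least at Day E + 29 when the sixth reaches Day 28, which is past Day 34 once E is 5 or later. Section 3.2.1.4 expects neutropenia to last well beyond 7 days, so in practice only the last two subjects can be cut short. With q = 0.30 × 29/35 = 0.2486 for two subjects, P = 0.458. With constant hazard, q = 1 − 0.7^(29/35) = 0.256 and P = 0.452. The shift is from 0.42 to about 0.45–0.46.

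**The case against.** The plan has real safeguards. Section 4.3 requires the Day 14, 21 and 28 assessments whether or not the subject has been discharged. Section 4.5.1 asks for every effort to follow dosed subjects, and section 5.5.1 follows them to Day 100. Potential DLTs must be notified within 24 hours. Investigators, sponsor and DSMB must all agree before escalation, and the DSMB may withhold it for any significant safety concern. These points reduce how often a subject would be lost, but they do not supply an evaluability rule. An event found after the review reaches the final tables too late for that escalation, and a DSMB cannot weigh what has not been observed.

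A reader might infer more than the documents support:

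- **That early leavers are declared DLT-free.** No passage says so. It follows from the replacement and MTD rules, and the Day 28 completion requirement can be read against it.
- **That the undercount grows with infusion duration.** The unobserved window grows only for the Day 28 review under the end anchor. For the 7-day rule the gap is constant or shrinks, and under the start anchor a Day 28 visit covers the window in every group.
- **That all six subjects are cut at Day 28.** This would give 0.54 in Group 4 and 0.64 in Group 5 (0.52 and 0.61 with constant hazard), but staggered enrolment rules it out in practice.
- **That Group 5 distorts an escalation.** It is the last group, so its 13-day gap bears only on the MTD statement, for which no day is fixed.
- **That discharged subjects go unseen from Day 28 to Day 100.** It is true that "Assessments scheduled on Days 35, 42 and 49 will be performed only for those subjects who are still hospitalized on those days". But Appendix 1 adds aGvHD grading on Days 56, 70 and 84 if possible, and the full Day 100 panel at any aGvHD of grade 2 or higher. Section 3.7 requires weekly CMV monitoring where subject or donor is seropositive.

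**Conclusion.** The point holds in this form. The window has no anchor, no subject is defined as DLT-evaluable, and the follow-up needed to avoid replacement is shorter than the window under both readings. The rule as written can therefore be applied to partly observed subjects, and its chance of being met is then higher than Table 2 states.

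At a 30% DLT risk the increase is about 0.05–0.07 for one subject lost at 7 days and 0.11–0.15 for two (uniform onset, end anchor). It is smaller under the start anchor in Groups 4 and 5. The early Day 28 review is a lesser issue: it exists under the end anchor, adds about 0.03–0.04 for Group 4 with two subjects cut short, and under the start anchor arises only if the visit falls on Day 25 or 26.

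The day counts come from the plan alone. The probabilities rest on assumed DLT risk, onset pattern and losses. They show a risk of undercounting at the decision point, not that DLTs will be undercounted.

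**What to change.** Reconcile sections 3.3.2, 3.3.3, 3.3.4, 3.5 and 4.5.1:

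1. State whether the 4-week window runs from the start or the end of infusion. The choice is the sponsor's.
2. Define a DLT-evaluable subject as one who had a DLT or was observed through the close of the window.
3. For the escalation and MTD counts, replace DLT-free subjects who were not so observed, or report them separately. Bring the 7-day replacement threshold into line with this.
4. Hold each group's DSMB review until the last subject's window has closed: Day 27 under the start anchor, or Day 30, 34 or 41 under the end anchor.

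Table 2 then describes the rule as run. The cost is protocol wording and an occasional extra replacement. Under the end anchor there is also a wait of about 6 days before Group 5 can open (up to 9 if the last visit falls on Day 25), and about 2 days (up to 5) after each of Groups 1–3. Under the start anchor the wait is at most 2 days.
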